5.3.5.11 Hospitalization or Prolonged Hospitalization

Any adverse event that results in hospitalization (i.e., in-patient admission to a hospital) or prolonged hospitalization should be documented and reported as a serious adverse event (per the definition of serious adverse event in Section 5.2.2), except as outlined below.

The following hospitalization scenarios are not considered to be adverse events:

- Hospitalization for respite care
- Planned hospitalization required by the protocol (e.g., for study drug administration or insertion of access device for study drug administration)

- Hospitalization for a pre-existing condition, provided that all of the following criteria are met:

The hospitalization was planned prior to the study or was scheduled during the study when elective surgery became necessary because of the expected normal progression of the disease

The patient has not experienced an adverse event

The following hospitalization scenarios are not considered to be serious adverse events, but should be reported as adverse events instead:

- Hospitalization for an adverse event that would ordinarily have been treated in an outpatient setting had an outpatient clinic been available (e.g., requirement for outpatient care outside of normal outpatient clinical operating hours)

5.3.5.12 Adverse Events Associated with an Overdose or Error in Drug Administration

An overdose is the accidental or intentional use of a drug in an amount higher than the dose being studied. An overdose or incorrect administration of study treatment is not itself an adverse event, but it may result in an adverse event. All adverse events associated with an overdose or incorrect administration of study drug should be recorded on the Adverse Event eCRF. If the associated adverse event fulfills seriousness criteria, the event should be reported to the Sponsor immediately (i.e., no more than 24 hours after learning of the event; see Section [5.4.2](#)).

No safety data related to overdosing of MHAA4549A are available; however, overdoses with a monoclonal antibody theoretically could cause volume overload that can result in edema and/or heart failure.

5.3.5.13 Patient-Reported Outcome Data

Adverse event reports will not be derived from PRO data by the Sponsor, and safety analyses will not be performed using PRO data. However, if any PRO responses suggestive of a possible adverse event are identified during site review of the PRO data, the investigator will determine whether the criteria for an adverse event have been met and, if so, will report the event on the Adverse Event eCRF.

5.4 IMMEDIATE REPORTING REQUIREMENTS FROM INVESTIGATOR TO SPONSOR

Certain events require immediate reporting to allow the Sponsor to take appropriate measures to address potential new risks in a clinical trial. The investigator must report such events to the Sponsor immediately; under no circumstances should reporting take place more than 24 hours after the investigator learns of the event. The following is a list of events that the investigator must report to the Sponsor within 24 hours after learning of the event, regardless of relationship to study drug:

- Serious adverse events (see Section [5.4.2](#) for further details)

- Adverse events of special interest (see Section 5.4.2 for further details)
- Pregnancies (see Section 5.4.3 for further details)

The investigator must report new significant follow-up information for these events to the Sponsor immediately (i.e., no more than 24 hours after becoming aware of the information). New significant information includes the following:

- New signs or symptoms or a change in the diagnosis
- Significant new diagnostic test results
- Change in causality based on new information
- Change in the event's outcome, including recovery
- Additional narrative information on the clinical course of the event

Investigators must also comply with local requirements for reporting serious adverse events to the local health authority and Institutional Review Board (IRB)/Ethics Committee (EC).

5.4.2 Reporting Requirements for Serious Adverse Events and Adverse Events of Special Interest

5.4.2.1 Events That Occur prior to Study Drug Initiation

After informed consent has been obtained but prior to initiation of study drug, only serious adverse events caused by a protocol-mandated intervention should be reported. The *paper Clinical Trial Serious Adverse Event/Adverse Event of Special Interest Reporting Form* provided to investigators should be completed and submitted to the Sponsor or its designee immediately (i.e., no more than 24 hours after learning of the event), either by faxing or by scanning and emailing the form using the fax number or email address provided *below*:

Region	Fax Number	Email Address
North America	[REDACTED]	[REDACTED]
EMEA	[REDACTED]	[REDACTED]
Asia Pacific	[REDACTED]	[REDACTED]

5.4.2.2 Events That Occur after Study Drug Initiation

After initiation of study drug, serious adverse events and adverse events of special interest will be reported until the patient *completes* the study at Day 100 or *discontinues early*. Investigators should record all case details that can be gathered immediately (i.e., within 24 hours after learning of the event) on the Adverse Event eCRF and submit the report via the electronic data capture (EDC) system. A report will be generated and sent to Safety Risk Management by the EDC system.

In the event that the EDC system is unavailable, the *paper Clinical Trial Serious Adverse Event/Adverse Event of Special Interest Reporting Form* provided to investigators should be completed and submitted to the Sponsor or its designee immediately (i.e., no more than 24 hours after learning of the event), either by faxing or by scanning and emailing the form using the fax number or email address provided *in Section 5.4.2.1*. Once the EDC system is available, all information will need to be entered and submitted via the EDC system.

Instructions for reporting post-study adverse events are provided in [Section 5.6](#).

5.4.3 Reporting Requirements for Pregnancies

5.4.3.1 Pregnancies in Female Patients

Female patients of childbearing potential will be instructed to immediately inform the investigator if they become pregnant during the study or within 120 days of study drug administration. A *paper Clinical Trial Pregnancy Reporting Form* should be completed and submitted to the Sponsor or its designee immediately (i.e., no more than 24 hours after learning of the pregnancy), either by faxing or by scanning and emailing the form using the fax number or email address provided *in Section 5.4.2.1*. Pregnancy should

not be recorded on the Adverse Event eCRF. The investigator should counsel the patient, discussing the risks of the pregnancy and the possible effects on the fetus. Monitoring of the patient should continue until conclusion of the pregnancy. Any serious adverse events associated with the pregnancy (e.g., an event in the fetus, an event in the mother during or after the pregnancy, or a congenital anomaly/birth defect in the child) should be reported on the Adverse Event eCRF. *In addition, the Investigator will submit a paper Clinical Trial Pregnancy Reporting Form when updated information on the course and outcome of the pregnancy becomes available.*

5.4.3.2 Pregnancies in Female Partners of Male Patients

Male patients will be instructed through the Informed Consent Form to immediately inform the investigator if their partner becomes pregnant during the study or within 30 days of study drug administration. A *paper* Clinical Trial Pregnancy Reporting Form should be completed and submitted to the Sponsor or its designee immediately (i.e., no more than 24 hours after learning of the pregnancy), either by faxing or by scanning and emailing the form using the fax number or email address provided in *Section 5.4.2.1*. Attempts should be made to collect and report details of the course and outcome of any pregnancy in the partner of a male patient exposed to study drug. The pregnant partner will need to sign an Authorization for Use and Disclosure of Pregnancy Health Information to allow for follow-up on her pregnancy. After the authorization has been signed, the investigator will *submit a paper Clinical Trial Pregnancy Reporting Form when updated information on the course and outcome of the pregnancy becomes available*. An investigator who is contacted by the male patient or his pregnant partner may provide information on the risks of the pregnancy and the possible effects on the fetus, to support an informed decision in cooperation with the treating physician and/or obstetrician.

5.4.3.3 Congenital Anomalies/Birth Defects and Abortions

Any congenital anomaly/birth defect in a child born to a female patient exposed to study drug or the female partner of a male patient exposed to study drug should be classified as a serious adverse event, recorded on the Adverse Event eCRF, and reported to the Sponsor immediately (i.e., no more than 24 hours after learning of the event; see *Section 5.4.2*). Any abortion should be reported in the same fashion (as the Sponsor considers abortions to be medically significant).

5.5 FOLLOW-UP OF PATIENTS AFTER ADVERSE EVENTS

5.5.1 Investigator Follow-Up

The investigator should follow each adverse event until the event has resolved to baseline grade or better, the event is assessed as stable by the investigator, the patient is lost to follow-up, or the patient withdraws consent. Every effort should be made to follow all serious adverse events considered to be related to study drug or trial-related procedures until a final outcome can be reported.

During the study period, resolution of adverse events (with dates) should be documented on the Adverse Event eCRF and in the patient's medical record to facilitate source data verification.

All pregnancies reported during the study should be followed until pregnancy outcome.

5.5.2 Sponsor Follow-Up

For serious adverse events, adverse events of special interest, and pregnancies, the Sponsor or a designee may follow up by telephone, fax, electronic mail, and/or a monitoring visit to obtain additional case details and outcome information (e.g., from hospital discharge summaries, consultant reports, autopsy reports) in order to perform an independent medical assessment of the reported case.

5.6 *ADVERSE EVENTS THAT OCCUR AFTER THE ADVERSE EVENT REPORTING PERIOD*

The Sponsor should be notified if the investigator becomes aware of any serious adverse event that occurs after the end of the adverse event reporting period (defined as 100 days after study drug administration), if the event is believed to be related to prior study drug treatment. *These events should be reported through the use of the Adverse Event eCRF. However, if the EDC system is not available, the investigator should report these events directly to the Sponsor or its designee, either by faxing or by scanning and emailing the Serious Adverse Event/Adverse Event of Special Interest Reporting Form using the fax number or email address provided to investigators.*

5.7 *EXPEDITED REPORTING TO HEALTH AUTHORITIES, INVESTIGATORS, INSTITUTIONAL REVIEW BOARDS, AND ETHICS COMMITTEES*

The Sponsor will promptly evaluate all serious adverse events and adverse events of special interest against cumulative product experience to identify and expeditiously communicate possible new safety findings to investigators, IRBs, ECs, and applicable health authorities based on applicable legislation.

To determine reporting requirements for single adverse event cases, the Sponsor will assess the expectedness of these events using the following reference document:

- MHAA4549A Investigator's Brochure

The Sponsor will compare the severity of each event and the cumulative event frequency reported for the study with the severity and frequency reported in the applicable reference document.

Reporting requirements will also be based on the investigator's assessment of causality and seriousness, with allowance for upgrading by the Sponsor as needed.

Certain adverse events are anticipated to occur in the study population at some frequency independent of study drug exposure and will be excluded from expedited reporting. These anticipated events include, but are not limited to, the following:

- Asymptomatic elevations of ALT, AST, and/or amylase without corresponding elevations of bilirubin have been shown to be increased during influenza A infection (Polakos et al. 2006; Yingying 2011).
- Influenza associated disease and/or complications of influenza

An IMC and SOC will monitor the incidence of the above-listed anticipated events during the study. An aggregate report of any clinically relevant imbalances that do not favor the test product will be submitted to health authorities.

6. STATISTICAL CONSIDERATIONS AND ANALYSIS PLAN

The database will be cleaned and locked when all patients have completed the study (Day 100) or discontinued.

The primary objective of this study is to characterize the safety and tolerability of a single dose of MHAA4549A as compared to placebo when administered in otherwise healthy patients with acute uncomplicated seasonal influenza A. Statistical summaries will be descriptive in nature (e.g., means, standard deviations, and percentiles). Patients will be grouped according to treatment actually received, and any patients who receive any amount of MHAA4549A or placebo will be included in the analyses.

All secondary efficacy analyses will be conducted according to the intent-to-treat principle and will include all patients who meet the following condition with patients allocated to the treatment arm to which they were randomized:

- Confirmation of influenza A from Day 1 pre-dose samples using a central PCR (to exclude false positives from local tests)

No formal hypothesis testing will be done in this study. As a result, no adjustment for type 1 error will be made to account for the multiplicity of analyses.

6.1 DETERMINATION OF SAMPLE SIZE

The planned sample size for this study is approximately 47 patients per treatment group. A total of approximately 141 patients will be enrolled in this study in order to obtain 120 evaluable patients (an estimated dropout rate of 15%).

The table below gives the probability of seeing an adverse event with a sample size of 40 per group. If the event occurs at a rate of $\geq 5\%$, the study has a $\geq 87\%$ chance of seeing at least 1 event in the dose group.

Table 5 Probability of Observing Adverse Events at Different Event Rates

Underlying “True Rate”	Probability of Seeing at Least 1 Event	Probability of Seeing at Least 2 Events
1%	33%	6%
5%	87%	60%
10%	99%	92%
15%	99%	98%

Note: Assumes that event rate follows a binomial distribution with p =AE rate and n =40 patients/arm.

6.2 SUMMARIES OF CONDUCT OF STUDY

The number of patients who enroll, discontinue (early discontinuation of treatment or early termination from the study), and complete the study will be tabulated by treatment group using descriptive statistics. Reasons for early discontinuation of treatment or early termination from the study will be listed and summarized by treatment group. Any eligibility criteria exceptions and other protocol deviations will also be summarized by treatment group.

6.3 SUMMARIES OF TREATMENT GROUP COMPARABILITY

Demographic and baseline characteristics of the patient will be summarized for all randomized patients by treatment group by use of descriptive statistics. Baseline is defined as the last available value prior to study drug administration. During the study patient disposition, concurrent treatment, and compliance with study treatment and visits will be summarized on the safety analysis population using descriptive statistics.

6.4 PRIMARY SAFETY ANALYSES

The safety analyses will include all randomized patients who received study drug, with patients grouped according to the treatment actually received. Safety parameters to be evaluated include adverse events (including deaths, serious adverse events, discontinuations due to adverse events, and the incidence and severity of adverse events), clinical laboratory tests, vital signs, and ECGs. All collected adverse event data will be listed by study site and patient number. All adverse events that occur on or after treatment on Day 1 will be summarized for each treatment group by mapped term, appropriate thesaurus levels, body system, and event within each body system, and toxicity grade. In addition, all serious adverse events, including deaths, will be listed separately and summarized. Serious adverse events caused by a protocol-mandated intervention (e.g., invasive procedures such as biopsies, discontinuation of medications) that occur between consent and first dose of study medication will be listed separately.

Laboratory data with values outside of the normal ranges will be identified. In addition, select laboratory data will be summarized by treatment group using descriptive summary statistics.

The absolute and percentage changes from baseline in vital sign parameters will be computed, and changes deemed clinically significant by the Investigator will be noted. Appropriate descriptive summary statistics will be provided for all vital sign parameters.

The prevalence (baseline) of ATA will be reported and correlation with PK, safety, efficacy, and *biomarker* endpoints will be analyzed as data allow.

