2. OBJECTIVES

2.1 PRIMARY OBJECTIVE

- To evaluate the safety and tolerability of a single IV dose of MHAA4549A as compared to placebo when administered in otherwise healthy patients with acute uncomplicated seasonal influenza A, focusing on the following:

Nature, frequency, and severity of serious and non-serious adverse events

Effects on laboratory values, vital signs, ECG parameters, and other safety biomarkers

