6.5 SECONDARY EFFICACY ANALYSES

The efficacy analyses will include all randomized patients who are confirmed to be influenza A infected, with patients grouped according to the treatment assigned at randomization. Efficacy parameters to be evaluated include duration and severity of influenza symptoms, hospitalization, and influenza-related complications.

Time to event data will be analyzed using Kaplan-Meier methodology and will be summarized using n, median when estimable, hazard ratios, and 95% confidence intervals. Patients who are lost to follow-up (while event free) will be censored at the time that they are last known to be event free.

Estimation of the treatment difference of proportions and its 95% confidence interval will be calculated using stratum-adjusted Mantel-Haenszel methodology ([Koch et al. 1989](#)). For continuous endpoints, Analysis of Covariance methods (after appropriate transformation of data) will be used to estimate treatment differences and 95% confidence intervals.

Other than censoring in the time to event analyses, no other imputation for missing data will be performed.

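### The primary objective compares safety with placebo, but Section 6.4 only describes each arm and plans no difference from placebo and no confidence interval

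*Combined protocol and SAP*

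**What the plan says.** The primary objective (Section 2.1) is comparative: "To evaluate the safety and tolerability of a single IV dose of MHAA4549A as compared to placebo". Section 6 restates it and sets the method: "Statistical summaries will be descriptive in nature (e.g., means, standard deviations, and percentiles".

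Section 6.4 defines the population and the grouping: "The safety analyses will include all randomized patients who received study drug, with patients grouped according to the treatment actually received". For adverse events it then says: "All adverse events that occur on or after treatment on Day 1 will be summarized for each treatment group by mapped term", followed by body system and toxicity grade. Serious adverse events are listed and summarized separately. Laboratory values outside the normal range are identified, selected laboratory data are summarized by group, and vital signs get descriptive statistics. The section names no difference between an active arm and placebo, no interval and no combined active group.

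Section 6.5, for secondary efficacy, says: "Estimation of the treatment difference of proportions and its 95% confidence interval will be calculated using stratum-adjusted Mantel-Haenszel methodology". For continuous endpoints, covariance analysis "will be used to estimate treatment differences and 95% confidence intervals". Time-to-event endpoints get hazard ratios and 95% intervals. Section 6.5 does not combine the two doses either.

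One policy covers both sections (Section 6): "No formal hypothesis testing will be done in this study".

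**The concern.** The trial's primary question is how each dose differs from placebo in safety, and the planned output never estimates that difference. The reader gets three columns of percentages and has to form the contrast by eye, without its uncertainty. With 40 to 47 patients per arm this can mislead in both directions: a chance imbalance may look like a signal, and equal counts may look like evidence of no difference.

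The contrast matters more than usual here because influenza itself produces events. Section 5.7 expects transaminase and amylase elevations and influenza complications to occur whether or not the patient received study drug, so attribution leans on the concurrent placebo arm. Section 3.1.4 asks the monitoring committees to judge toxicity imbalance against placebo, and Section 5.7 has clinically relevant imbalances reported to health authorities. Neither names a statistic.

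**Working it through.** **1. The plan's own figures (Section 6.1, Table 5).** Inputs: n = 40 per arm, binomial. P(at least 1) = 1 − (1−p)^40; P(at least 2) = 1 − (1−p)^40 − 40p(1−p)^39.

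| True rate | At least 1: computed (plan) | At least 2: computed (plan) |
|---|---|---|
| 1% | 33.1% (33%) | 6.1% (6%) |
| 5% | 87.1% (87%) | 60.1% (60%) |
| 10% | 98.5% (99%) | 92.0% (92%) |
| 15% | 99.9% (99%) | 98.8% (98%) |

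The table reproduces; the last row is truncated rather than rounded. The sample size also agrees: 120/0.85 = 141.2, and 141 × 0.85 = 119.9. All of this concerns detection within a single group. None of it says how precisely a difference from placebo would be estimated.

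**2. Precision of the missing contrast.** Inputs: 1:1:1 allocation (Section 3.1.1), and 47 enrolled or 40 evaluable per arm (Section 6.1). Because the safety set includes anyone who received any amount of a single infusion, its denominator should be nearer 47; both are shown. The documents give no placebo adverse event rate for this population, so the rates are assumptions, taken as equal in both arms.

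Wald 95% half-width = 1.96 × √(p(1−p)/n₁ + p(1−p)/n₀).

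Worked case at 10% and 47 per arm: 1.96 × √(2 × 0.10 × 0.90/47) = 0.121, or ±12.1 points.

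| Assumed rate | One dose vs placebo, 47 per arm | 40 per arm |
|---|---|---|
| 5% | ±8.8 | ±9.6 |
| 10% | ±12.1 | ±13.1 |
| 50% | ±20.2 | ±21.9 |

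For the any-event category the only figures to hand come from healthy volunteers (Section 1.2.2): 60.0% and 83.3% on placebo in the two Phase 1 studies, and 86% across all groups in the challenge study. At 60% and 86% with 47 per arm the formula gives 1.96 × √(2 × 0.60 × 0.40/47) = ±19.8 points and 1.96 × √(2 × 0.86 × 0.14/47) = ±14.0 points, inside the range above.

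**3. Effect of pooling.** With 2n active patients against n on placebo, the ratio of half-widths is √((1/(2n) + 1/n)/(2/n)) = √0.75 = 0.866, about 13% narrower. At 10% this takes ±12.1 to ±10.5 (94 vs 47), or ±13.1 to ±11.4 (80 vs 40).

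**4. What a reader would see.** Take illustrative counts of 6/40 on one dose and 2/40 on placebo: 15% against 5%, a difference of +10 points. The Newcombe 95% interval, built from the two Wilson score intervals (7.1% to 29.1% and 1.4% to 16.5%), is:
- lower: 10 − √((15 − 7.1)² + (16.5 − 5)²) ≈ −4.0;
- upper: 10 + √((29.1 − 15)² + (5 − 1.4)²) ≈ +24.5.

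The two percentages alone suggest a threefold excess; the interval shows that no difference and a large excess are both compatible with the data.

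**The case against.** The strongest reply is that descriptive safety reporting is a declared choice. The study calls itself exploratory (Section 1.3) and hypothesis-generating (Section 6.10.1). Its primary outcome is the incidence, nature and severity of events (Section 3.4.1), and tables with a concurrent placebo column deliver that. A comparative objective does not by itself demand an interval, and no stated decision rule depends on one. This stands to the extent that the plan is not in error. It does not explain the gap, because efficacy falls under the same no-testing policy and still gets differences with intervals.

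Four stronger readings are tempting, and the documents do not support them:

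- A reader might infer that Section 6.5 pools the doses and that Section 6.4 falls short of it on that point too. Section 6.5 specifies no pooled contrast; the asymmetry covers the difference and the interval only.
- A reader might infer that safety is never compared with placebo. The committees assess imbalance (Sections 3.1.4 and 5.7), but this is monitoring without a named statistic. Hospitalization, influenza-related death and complications do get differences with intervals, but as efficacy endpoints in PCR-confirmed patients grouped as randomized, not in the as-treated safety population.
- A reader might infer that a pooled column would make uncommon events easier to detect. The number of patients dosed fixes the chance that a case occurs, and Section 6.4 already lists every collected event. Pooling only narrows the interval.
- A reader might infer that pooling is free. Section 3.3.1 chose 8400 mg to separate nasal exposure from 3600 mg, so a pooled estimate can dilute an effect limited to one dose.

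It is also fair to say that a set of unadjusted intervals may be read as informal tests. That is a real drawback, and it argues for a short list and clear labelling.

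**Conclusion.** The concern holds as a weakness of the analysis plan: a comparative primary objective is given only per-arm description, while secondary efficacy is given differences with 95% intervals. It is neither a contradiction nor a wrong number; Table 5 and the sample size reproduce.

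Its size is the uncertainty left unshown: roughly ±9 to ±20 points for one dose versus placebo at 47 per arm, or ±10 to ±22 at 40. These figures assume true rates between 5% and 50%, equal in both arms, and the Wald approximation without stratification. That approximation is rough at 5%, where only two or three events per arm are expected, so they indicate scale and are not the intervals to report. The change is worth making because it lets the trial answer its own question at little cost. It does not affect trial conduct.

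**What to change.** Add to Section 6.4, in the as-treated safety population, the risk difference versus placebo with a two-sided 95% interval by a score or exact method, for each dose separately. Count patients with at least one event in:

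- any adverse event;
- any Grade 3 or higher adverse event;
- any serious adverse event;
- any adverse event of special interest;
- any Grade 3 or higher treatment-emergent laboratory abnormality.

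State that these are estimates without testing, are not adjusted for multiplicity, and will be wide. A pooled-dose contrast may stand beside the per-dose contrasts as a supplement, with a note that it can hide an effect limited to one dose.

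The cost is a few table columns: 5 categories × 2 doses = 10 intervals, or 15 with the pooled supplement. No new data are needed and the no-testing policy is unchanged. The downside is that readers may treat some of these intervals as tests, which the label and the short list should limit.
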